4. CLINICAL INVESTIGATION OBJECTIVES

4.1 Overall Objective

The study aim is to investigate the diagnostic accuracy of the High-Resolution OCT in comparison with conventional imaging methods and whether High-Resolution OCT can reliably diagnose retinopathies thereby making more invasive investigations such as fluorescein angiography or conventional imaging methods futile. The main goal is to facilitate diagnosis of eye diseases for individual patients.

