6. CLINICAL INVESTIGATION DESIGN

6.1 General clinical investigation design and justification of design

This trial is a prospective clinical study. Patients, who fulfilled the inclusion criteria will be recruited at the Inselspital Bern. Study data will be collected in REDCap®, a secure, and validated web application for building and managing online surveys and databases. Study participants will undergo imaging of one or both eyes in accordance with the clinical indication, which will last approximately 30-60 seconds per eye. The imaging process is without any contact and pharmacologic dilatation of the pupils will not be used for the purposes of this study.

We plan to include approximately 550 participants in the study, including 100 healthy participants and 450 patients with diagnosed ocular disorders, including diabetic retinopathy (50 patients), artery and vein occlusion (50 patients), glaucoma (50 patients), optic nerve neuropathy (50 patients), hereditary retinal diseases/dystrophies (50 patients), retinal detachment (50 patients), age related macular degeneration (50 patients), retinal changes from arterial hypertension (50 patients), uveitis (50 patients).

Study participants will undergo imaging with High-Resolution OCT only within a single imaging session on a single day. Additionally, study participants will be asked to consent to prospective collection of clinical and demographic data, to correlate findings of High-Resolution OCT imaging to subsequent clinical course. Data from the clinical records are to be used for the study up to the time of the visit.

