7.2 Recruitment and screening

There will be a consecutive ongoing recruitment of patients and healthy subjects attending routine follow-ups through the involved investigators in daily clinical practice at Department of Ophthalmology, Inselspital, Bern. Recruitment will last from October 2021 to November 2023. Subjects will be given enough time (hours to days) to consider and to council with relatives and experts. No screening requirements is necessary (laboratory or other diagnostic tests). There will be no payment or compensation given to subjects.

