11.4.2 Primary Analysis

The results will be displayed using a receiver operating characteristic (ROC), or ROC curve. The curve is created by plotting the true positive rate (TPR) against the false positive rate (FPR) at various threshold settings. Here the required total sample size for estimating sensitivity (presence of the pathological changes within the scans) with respect to marginal error (0.03), sensitivity (90%) and the prevalence (0.9) of disease in target population would be approximately 550 subjects¹⁷. Depending on the results, precision and recall (PR) curves are also going to be computed, which are useful in case of distribution imbalance between two classes of a binary model, specifically if the true negative values are high, the latter not being taken into account in the calculation³⁰. Precision (Y-axis) is referred as the positive predictive value and recall (X-axis) as sensitivity. A high precision value means that the tested classifier/device provides accurate results, while high recall indicates that the majority of all positive samples were detected. The possible AUC value ranges from 0.5 (discriminative performance equal to chance) to 1.00 (perfect discriminative performance). The primary analysis will be done using

Python 3 and its open-source package Scikit-learn v0.20.3.

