11.4.3 Secondary Analyses

Subgroup analysis will be performed to differentiate different disease entities using non-parametric test with a significance level of 0.05, with patients suffering from diabetic retinopathy, glaucoma, optic nerve neuropathy, hereditary retinal diseases, retinal detachment, artery and vein occlusion, age related macular degeneration, retinal changes from arterial hypertension and uveitis. In order to compare these groups with conventional imaging and controlling for some degree of variation due to age, we estimate a group size of approximately 50 patients and 100 healthy subjects ¹⁶.

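### Section 11.4.2 reads high precision as proof of an accurate device, but precision and the PR curve depend on a case mix largely set by the recruitment targets, and the 0.5 chance level is not tied to the ROC AUC

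*Combined protocol and SAP*

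**What the plan says.** Section 6.1 sets the intended sample: "We plan to include approximately 550 participants in the study, including 100 healthy participants and 450 patients with diagnosed ocular disorders". Section 11.4.3 repeats the targets by disease group: "we estimate a group size of approximately 50 patients and 100 healthy subjects". Section 7.2 calls recruitment consecutive and does not say how the group targets will be filled.

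Section 11.4 plans both a ROC curve and a precision-recall (PR) curve. Section 11.4.2 makes the PR curve conditional on what the results show, defines precision as the positive predictive value and recall as sensitivity, and gives a rule for reading it: "A high precision value means that the tested classifier/device provides accurate results". The PR curve is justified by class imbalance, "specifically if the true negative values are high, the latter not being taken into account in the calculation". The next statement on scale is: "The possible AUC value ranges from 0.5 (discriminative performance equal to chance) to 1.00". It follows the PR text directly and does not say which curve it refers to.

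The primary outcome (sections 5.1 and 9.2.1) is sensitivity and specificity against conventional imaging. Section 9.2.1 adds a separate binary result for each type of pathological change. The only prevalence stated is 0.9, in the sample-size sentence of section 11.4.2.

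**The concern.** Sensitivity and specificity describe the test within diseased and non-diseased subjects. Precision mixes the two with the share of positives in the sample. Where that share is high, precision is high even for a test that does not discriminate, so it cannot by itself show accuracy. Here the share follows mainly from the recruitment targets, and the plan gives no caveat about case mix, no baseline for the PR curve and no recalculation at another prevalence.

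Two misreadings are possible. First, a large precision figure could be taken as good performance when it mostly reflects the mix, or be carried over to practice; section 4.1 says "The main goal is to facilitate diagnosis of eye diseases for individual patients". Second, a PR AUC could be judged on a scale that starts at 0.5, on which an uninformative test would look respectable.

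**Working it through.** **The plan's own figures.** The plan states no precision or PR AUC to reproduce. The nearest figure is the 550 that section 11.4.2 attaches to sensitivity 0.90, margin 0.03 and prevalence 0.9. The usual formula, N = z² × Se(1 − Se)/d²/prevalence, gives 1.96² × 0.09/0.0009/0.9 = 384.1/0.9, about 427 at two-sided 95% (301 at 90%, 738 at 99%). So 550 does not reproduce from the stated inputs. That is a separate question, and nothing below depends on it.

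**Inputs.** 450 diagnosed and 100 healthy (6.1); sensitivity 0.90 (assumed in 11.4.2); prevalence 0.9 (11.4.2). Specificities of 0.90 and 0.50 are illustrative. Prevalences of 0.50 and below are assumptions, because the documents give no clinic prevalence.

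**Step 1: share of positives.** 450/550 = 81.8%, if every diagnosed patient counts as positive and every healthy subject as negative.

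**Step 2: precision at that mix.** Precision = TP/(TP + FP).
- Flag everyone: 450/(450 + 100) = 81.8%, with recall 100%.
- Se 0.90, Sp 0.90: 405/(405 + 10) = 97.6%.
- Se 0.90, Sp 0.50: 405/(405 + 50) = 89.0%.
- Se 0.90, Sp 0.10 (no discrimination): 405/(405 + 90) = 81.8%.

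A 40-point loss of specificity costs 97.6 − 89.0 = 8.6 points of precision.

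**Step 3: the same devices at other prevalences.** Precision = Se·p/(Se·p + (1 − Sp)(1 − p)), with Se = 0.90.

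| Prevalence p | Sp 0.90 | Sp 0.50 | Flag everyone |
|---|---|---|---|
| 0.90 (stated in 11.4.2) | 98.8% | 94.2% | 90.0% |
| 0.818 (targets) | 97.6% | 89.0% | 81.8% |
| 0.50 (assumed) | 90.0% | 64.3% | 50.0% |
| 0.30 (assumed) | 79.4% | 43.5% | 30.0% |
| 0.20 (assumed) | 69.2% | 31.0% | 20.0% |
| 0.10 (assumed) | 50.0% | 16.7% | 10.0% |

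**Step 4: a per-lesion readout.** Suppose a lesion is present in 50 of 550 subjects (an assumption). The baseline is 50/550 = 0.09. With Se 0.90, precision is 45/(45 + 50) = 47.4% at Sp 0.90 and 45/(45 + 250) = 15.3% at Sp 0.50. For one disease group of 50 against the 100 healthy, the baseline is 50/150 = 0.33.

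**Step 5: chance AUC.** With random scores (3,000 simulated data sets per mix), mean PR AUC was 0.820 for 450:100 (95% range 0.79 to 0.85), about 0.10 for 50:500 and about 0.35 for 50:100. Mean ROC AUC was 0.50 in all three. Chance PR AUC therefore follows the share of positives; chance ROC AUC does not.

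**The case against.** The strongest reply is that none of this reaches the primary result. Sensitivity and specificity are already the primary outcome, the ROC curve plots the false positive rate directly, and the formal comparison in section 11.4 is a one-sided 95% confidence interval on the difference from conventional imaging. The PR curve is only a display. That stands, and it limits the point to interpretation and reporting. A reader might infer that poor specificity would go unseen or that the primary analysis is invalid; the documents support neither.

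A second reply is that 82% is not the prevalence of every readout. That also stands. It is the patient-level share of diagnosed against healthy subjects, the group sizes are approximate, recruitment is called consecutive, and section 9.2.1 takes one binary result per lesion type. A reader might infer that prevalence is fixed at 82% throughout, or that the many-true-negatives reason for the PR curve is backwards. For an uncommon lesion that reason can fit, and low precision would then expose poor specificity. It fits badly only for the diseased-versus-healthy readout.

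Third, a chance level of 0.5 is correct for the ROC AUC at any case mix. A reader might infer that the stated value is plainly wrong; the defect is that the curve is not named. The documents also describe binary readouts and no graded score, so the area may have little content. The no-skill level of precision is the share of positives in either case.

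Fourth, precision in the sample need not flatter the device: at the protocol's own 0.9 it would be slightly higher than at 81.8%. The falls at lower prevalence rest on assumed values. This argues for showing a range and does not support the sentence in 11.4.2, since flagging everyone at 0.9 gives precision 90%.

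Finally, two modalities read on the same subjects share one prevalence, so comparing their precision within the sample is fair in direction. The sentence in question, however, is about the absolute value.

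**Conclusion.** The point holds as one of interpretation in the primary-analysis section. With the planned mix, a high precision does not show that the device is accurate: 81.8% is reached with no discrimination, and 89.0% with specificity of only 50% at 90% sensitivity. These figures assume a patient-level readout in which diagnosed patients are the positives and the targets of about 450 and 100 are met. For per-lesion readouts the baseline is unknown and may be far lower, for example 0.09 if 50 of 550 are positive. Baselines from 0.09 to 0.82 within one study mean that no precision value can be read without its share of positives.

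The AUC scale is right for ROC and wrong if applied to PR, and the text leaves open which is meant. The formal comparison and the sensitivity and specificity estimates are not directly affected. A reader might conclude that the PR curve has to be removed; that would be a preference, because a labelled baseline is enough.

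**What to change.** In section 11.4.2:

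- Delete the sentence equating high precision with accurate results, or qualify it by saying that precision depends on the share of positives and that sample precision reflects the recruitment mix.
- State that the 0.5 chance level applies to the ROC AUC only.
- If a PR curve is shown, draw its no-skill line at positives/N for that particular analysis, and always present it with sensitivity and specificity.
- If predictive values are reported, calculate them from the estimated sensitivity and specificity over a stated range of prevalences, including the protocol's assumed 0.9 and lower values.

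The cost is a few sentences and one short table, with no change to recruitment or procedures. The downside is that predictive values may look less favourable at the lower prevalences.

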11.4.3 Secondary Analyses

Subgroup analysis will be performed to differentiate different disease entities using non-parametric test with a significance level of 0.05, with patients suffering from diabetic retinopathy, glaucoma, optic nerve neuropathy, hereditary retinal diseases, retinal detachment, artery and vein occlusion, age related macular degeneration, retinal changes from arterial hypertension and uveitis. In order to compare these groups with conventional imaging and controlling for some degree of variation due to age, we estimate a group size of approximately 50 patients and 100 healthy subjects ¹⁶.

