
Duration of the investigation:
	
Last participant processed and finishing the study : 30.11.2023

Investigation schedule:
	
31.October 2021
 
30. November 2023

Investigator(s):	
[name]. [name] [name]. [name] [name]. [name] [name] PhD. [name] [name] [name] [name] [name]
 
Universitätsklinik für Augenheilkunde Inselspital [name] Telefon [name]

Investigational Site(s):	
Single center study at Universitätsklinik für Augenheilkunde Inselspital, Bern

Statistical considerations:	
The primary variable for this assessment is the ability to detect retinal morphological changes with High-Res-OCT in comparison to conventional ophthalmic imaging methods such as OCT, color fundus photography and fluorescein angiography. This will result in a binary outcome. Assuming that the accuracy of each of these conventional imaging modalities separately is 90%, and there is truly no difference between the conventional imaging and High-Res-OCT, then 550 patients are required to be 90% sure that the upper limit of a one-sided 95% confidence interval (or equivalently a 90% two-sided confidence interval) will exclude a difference in favour of the conventional imaging of more than 10% ^{16,17}.
 
Subgroup analysis will be performed to differentiate different disease entities using non-parametric test with a significance level of 0.05.
 
Descriptive analyses will evaluate demographic data as well as visual acuity data separately for each group of patients.
 
Subgroup analysis will be performed with patients suffering from diabetic retinopathy, artery and vein occlusion, optic nerve neuropathy, glaucoma, retinal detachment, age related macular degeneration, retinal changes from arterial hypertension and uveitis. In order to compare these groups with conventional imaging and controlling for some degree of variation due to age, we estimate a group size of approximately 50 patients and 100 healthy subjects.

Compliance statement:	
This investigation will be conducted in compliance with the CIP, the current version of the Declaration of Helsinki, ISO14155, ICH-GCP (as far as applicable) as well as all national legal and regulatory requirements.

ABBREVIATIONS

Provide a list of abbreviations used in the CIP – to be completed/adapted

AE	Adverse Event
ADE	Adverse Device Effect
ASADE	Anticipated Serious Adverse Device Effect
ASR	Annual Safety Report
CEC	Competent Ethics Committee

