9.2.2 Assessment of secondary outcomes

- To evaluate whether pathological changes seen in SD-OCT or color fundus photography correlate with changes seen in High-Res-OCT, a binary readout will be used, i.e. pathology present yes/no.
- Subgroup analysis will be performed with patients suffering from diabetic retinopathy, artery and vein occlusion, retinal detachment, glaucoma, optic nerve neuropathy, hereditary retinal diseases, age related macular degeneration, retinal changes from arterial hypertension and uveitis. For this purpose a quantification and classification of the pathological changes in relation to each disease will be performed, among them; Drusen classification according to Age-Related Eye Disease Study (AREDS) ²⁷, neovascularization, bleeding, ischemia, atrophy, exudate, retinal thickness, intra-subretinal fluid, pigment epithelial detachment (PED) and epiretinal membrane ^{28,29}. In order to compare these groups with conventional imaging and controlling for some degree of variation due to age, patients included in subgroup analysis will be compared to a pool of healthy subjects.
- Evaluation of the intra- and inter-reader reproducibility in the diagnosis using High-Res-OCT. This will result in a binary outcome (diagnosis present or absent). The evaluation of the inter-reader reproducibility in healthy subjects with High-Res-OCT will be assessed. For this purpose a senior physician, a resident and an expert physician will subsequently analyze the images.
- Furthermore the quality of the segmentation of the retinal layers, i.e. the discrimination capacity between the different layers (internal limiting membrane, retinal nerve fibre layer, ganglion cell layer, inner plexiform layer, inner nuclear layer, outer plexiform layer, outer nuclear layer, external limiting membrane, photoreceptor layer, retinal pigment epithelium, Bruch's membrane, choriocapillaris and choroidal stroma) will be assessed, especially in the healthy group. For this purpose, a binary outcome will also result, i.e. discrimination between each layer possible, yes or no.

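### The disease-subgroup analysis is meant as a comparison with conventional imaging, but no stated contrast compares the devices within a disease, and the tests are uncounted and unadjusted

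*Combined protocol and SAP*

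**What the plan says.** Section 11.4.3 (Secondary Analyses) sets the test and its level: "Subgroup analysis will be performed to differentiate different disease entities using non-parametric test with a significance level of 0.05". It lists nine disease groups. It then explains the numbers with "In order to compare these groups with conventional imaging and controlling for some degree of variation due to age", followed by "we estimate a group size of approximately 50 patients and 100 healthy subjects".

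Section 9.2.2 (Assessment of secondary outcomes) repeats the aim of comparing the groups with conventional imaging, but completes the sentence with a different contrast: "patients included in subgroup analysis will be compared to a pool of healthy subjects". It also lists several features to be quantified or classified for each disease, without saying which of them are tested.

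The Statistical considerations row of the synopsis gives eight groups, leaving out hereditary retinal diseases: "diabetic retinopathy, artery and vein occlusion, optic nerve neuropathy, glaucoma, retinal detachment, age related macular degeneration, retinal changes from arterial hypertension and uveitis".

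No section names the non-parametric test, the tested variable, the number of tests or a multiplicity adjustment, and none labels these analyses exploratory.

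**The concern.** The aim and the stated contrasts do not match. A patient-versus-healthy comparison on High-Res-OCT shows how a disease looks beside health. Participants are assigned to a group by diagnosis or categorised as healthy (sections 6.1 and 7.3), so some difference is to be expected from how the groups are formed. A disease-versus-disease test shows whether diseases differ from one another. Neither says whether High-Res-OCT finds more or less than SD-OCT in, for example, diabetic retinopathy.

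The disease subgroups are listed as a secondary outcome (section 5.2), so readers will look for device statements by disease. An analyst following the text could produce p-values below 0.05 for each group and still have no result on that question. Error control matters as well: section 11.4.1 makes a follow-on longitudinal study depend on significant data, and section 11.4.5 lets the analysis be adapted as questions arise.

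**Working it through.** **1. The plan's own figure.** The group sizes add up: 9 × 50 + 100 = 550. No effect size or power is given for 50 against 100, so the choice of 50 cannot be reproduced from the text.

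**2. What the text allows.**

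| Contrast | Where it appears | Compares devices within a disease? |
|---|---|---|
| Disease v disease | 11.4.3, purpose of the test | No |
| Patients v healthy pool | 9.2.2 | No |
| Groups v conventional imaging | 9.2.2 and 11.4.3, as an aim only | Yes, but no variable, pairing or test is attached |

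**3. False-positive rate across the groups.** Inputs are a level of 0.05 and nine groups, both from section 11.4.3. One test per group, two-sided, is an assumption. All rates suppose that every null hypothesis is true.

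- Nine independent tests: 1 − 0.95^9 = 0.370.
- Eight independent tests (the synopsis list): 1 − 0.95^8 = 0.337.
- Nine groups of 50 against one shared pool of 100: the correlation between any two test statistics is (1/100) / (1/50 + 1/100) = 1/3. Integrating over the shared component gives 0.318. A simulation of nine Mann-Whitney tests (4,000 runs) gave 0.3225.
- One omnibus test: 0.05.
- All 9 × 8 / 2 = 36 pairwise disease contrasts: about 0.57, by simulation.

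The text does not choose among these. Testing several features per disease would add further tests.

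**4. What a group of 50 can support for the device contrast.** Inputs are 90% accuracy, a 10-point margin and a one-sided 95% limit, all from section 11.2. The discordance between devices is not given, so two values are assumed: 2 × 0.9 × 0.1 = 0.18 (errors independent between devices) and 0.10. All 50 patients are assumed to have both scans, and the true difference is zero.

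Power = Φ(0.10 / √(discordance / 50) − 1.645)

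- Discordance 0.18: √(0.18/50) = 0.0600; 0.10/0.0600 − 1.645 = 0.022; power 51%.
- Discordance 0.10: √(0.10/50) = 0.0447; 0.10/0.0447 − 1.645 = 0.591; power 72%.

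The 95% half-width on the paired difference is 1.96 × 0.0600 = 11.8 points or 1.96 × 0.0447 = 8.8 points. For a single sensitivity of 90% it is 1.96 × √(0.09/50) = 8.3 points.

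**5. What adjustment costs.** Holm's strictest step over nine groups is 0.05/9 = 0.0056. With all discordant pairs in one direction, the two-sided exact McNemar p-value is 2 × 0.5^k. Six pairs give 0.031, eight give 0.0078 and nine give 0.0039. The most extreme group would need 9–0 instead of 6–0.

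**The case against.** The strongest defence is that the device comparison is not missing from the plan. It is the primary analysis (sections 11.1 and 11.4), and the first item in section 9.2.2 sets SD-OCT or colour fundus findings beside High-Res-OCT findings. That stands. A reader might infer that the trial never compares the devices; the documents do not support this, and the gap is confined to statements by disease.

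Three other strong readings are tempting.

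- **That the plan runs nine tests against the healthy pool with a 37% error rate.** The healthy pool comes from section 9.2.2, where the sentence also mentions conventional imaging and age. The 0.05 test in section 11.4.3 is described as separating diseases. The count of nine is an inference, and 37% requires independence, which a shared pool does not give.
- **That significance is nearly guaranteed in every group.** The documents give no expected frequencies, and features such as epiretinal membrane or drusen need not differ from healthy subjects in every disease. Nor can near-certain true differences and a rate that supposes every null to be true describe the same tests.
- **That every participant has a High-Res-OCT and SD-OCT pair.** Section 9.1 accepts SD-OCT, fundus photography or fluorescein angiography according to routine, section 12.1.2 records SD-OCT where applicable, and section 6.1 allows one or both eyes. The share with a same-eye pair is unknown.

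It is also fair to say that secondary subgroup analyses need not control the family-wise rate if they are labelled exploratory. That stands too, but the plan gives no such label.

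**Conclusion.** The point holds in this form: the stated subgroup contrasts do not match the stated aim, and as written they cannot support a device statement for any single disease. The contrast, the variable and the number of tests are undefined, and there is neither multiplicity control nor an exploratory label.

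The error rate of about 32% to 37% is conditional on nine two-sided tests with every null true. It would be 5% for one omnibus test and about 57% for all pairwise contrasts. The power range of 51% to 72% rests on assumed discordance and on 50 complete pairs per group. With fewer pairs it falls, so the groups suit estimation and not per-group non-inferiority claims.

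This should be corrected before analysis. It affects secondary claims and leaves the primary comparison untouched.

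**What to change.** Amend sections 9.2.2 and 11.4.3, and align the synopsis on nine groups.

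- Within each disease group, analyse patients who have both High-Res-OCT and SD-OCT of the same eye, with one study eye per patient (section 12.1.2 already records a study eye). Report the number of pairs per group.
- Report the paired difference, High-Res-OCT minus SD-OCT, in detection of pathology (present or absent) with a 95% confidence interval. Name one such readout per group so that the number of tests is fixed. State that a difference in detection is not a difference in accuracy unless a reference standard is defined.
- Give exact McNemar p-values, either Holm-adjusted across the nine groups or labelled exploratory. Either is acceptable; choose one in advance.
- Describe the groups of about 50 as estimation, with no per-group non-inferiority claim.
- Keep patient-versus-healthy contrasts as descriptive.

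The cost is wording only; no extra patients or visits are needed. The downsides are wide intervals, stricter thresholds if Holm is chosen, and fewer than 50 pairs where routine imaging did not include SD-OCT. Guaranteeing a pair for everyone would mean changing the procedures in section 9.1, which this fix does not require.
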